8.4.1 Scale Calibration

In order to monitor the calibration of the scales over time, each team will weigh a 5 kg test weight at the beginning and end of the day. This measurement will take place at the site of the scale storage so that the weights do not need to be carried to the field. In some cases, these weights will be kept in a project vehicle.

9.5 Measuring Mid-Upper Arm Circumference (MUAC)

[figure not shown]
The child's MUAC will be measured one time. MUAC measurements will be taken at the midpoint of the left arm between the tip of the shoulder and the tip of the elbow using non-stretch MUAC tapes.

First, find the approximate midpoint of the upper arm. Have the child stand up straight with feet together, and the right arm bent 90 degrees at the elbow, palm facing up. The examiner is positioned behind the child. If it is helpful, mark the midpoint with a permanent marker. To measure mid-upper arm circumference, have the child stand up straight with the arms relaxed at the sides. The examiner will stand

facing the child's right side. The measuring tape is placed around the upper arm at the marked point. Wrap the tape around the arm, pulling it to lie flat against the surface of the skin. Be careful not to pull the tape too tightly (to compress the skin).

The line for reading measurements is clearly labeled on the MUAC tape (READ (cm)). Read the number aligned with the measurement line on the tape Upon measuring, the examiner will clearly call out the number to the recorder. Record to the nearest 0.1 cm (0.1 cm = 1 mm). Keeping the child in place, release the MUAC strip.

If the MUAC is <11.5cm refer the child to the nearest health center.

10 Chapter 10: Vital Status

Vital status will be recorded at all follow-up visits, including whether the child is alive, has died, or has moved. Date of death and location of move will be recorded.

11 Chapter 11: Data Collection, Management, and Security

11.1 Data Collection

Data will be collected on enrolled children at baseline (time of enrollment), and follow-up at days 14 and 180. Written informed consent will be collected on paper and the study nurse will administer the treatment letter based on the tablet app. All data will be collected electronically on mobile devices using a mobile application.

11.2 Data Management and Security

Electronic data will be uploaded daily to a secure, password-protected, cloud-based server. All devices used for data collection will be password-protected, as will the mobile application itself. Paper forms will be stored in locked cabinets accessible only by specific study team members at each enrollment site. No identifiers will be collected electronically. Study data will only be accessible by study team members and investigators in order to protect confidentiality.

11.3 Data Quality and Monitoring

All study team members collecting data will undergo an initial training to learn how to use the mobile devices as well as best practices for data collection. Data collection will be monitored on a weekly basis by the study team. Concerns over data quality and completeness will be relayed to the local study team by email, and refresher trainings and/or additional supervision of data collection by local investigators will be planned as needed. The study team will send quarterly progress reports to the DSMC, including aggregate data on enrollment and follow-up status and adverse events.

12 Chapter 12: Protection of Human Subjects

Before the study begins, each site will obtain formal ethical approval from their respective national ethics committee. In addition, local staff will approach community leaders to describe the study and answer any questions. Study staff will proceed only if local leadership consents to participate. We will obtain written informed consent for each child's participation from their parent or guardian. If, at any time, a parent or guardian elects to withdraw a family member from the study, they will be free to do so. Children with wasting or stunting will be referred for appropriate treatment by trained study personnel to the nearest health center.

12.1 Institutional Review Board Approval

University of California, San Francisco (UCSF) Committee on Human Research UCSF's Committee on Human Research will annually review the study protocol for ethical approval.

Comité d'Ethique du Burkina Faso

The study protocol will be reviewed and granted ethical approval by the Comité d'Ethique du Burkina Faso before any study activities begin.

12.2 Informed Consent

Study personnel fluent in relevant local languages will approach parents or guardians of eligible children. In a private setting, the study team member will explain the objectives, risks, and benefits of the study as well as detailed information about what study participation entails for the child and the parent or guardian. The study team member will clarify that participation in the study is voluntary, that participation may be stopped at any time, and that all collected data will be kept confidential and securely stored. The study team member will ensure comprehension by inviting the parent or guardian to ask questions and will provide time for the parent or guardian to consider participation. When providing consent, both the study team member and the parent or guardian will sign two copies the consent document. One copy will be given to the parent or guardian and the other will be kept for study reference.

12.3 Risks and Benefits of Study Procedures

11.3.1 Procedures

Nasopharyngeal swabs: There are minimal risks to the participant who receives nasopharyngeal swabbing. Participants may experience some temporary discomfort, but the swabbing involves minimal risk. Any adverse effects, such as nose-bleeds, will be treated immediately by the examiners. Other health care will be provided at no cost to the study participant if necessary to address a study-related adverse health event.

Stool samples: Fresh frozen stool collection is a simple procedure with very minimal risk. Stool sample collection is a non-invasive procedure with no associated risks.

Anthropometric Measurements: There are minimal risks associated with the measuring board, scale, or MUAC tapes aside from anxiety during the measurements. Examiners will do their best to ensure that the parent/guardian of the child understands the process of assessing anthropometric measurements. The examiners will attempt to minimize discomfort for all study participants before, during, and after the measurements are taken. Children with wasting or stunting will be referred for appropriate treatment at the nearest health center.

Venipuncture: The standard risks of drawing blood from a vein include discomfort at the site of the puncture, bruising, swelling around the site, and rarely infection. Trained staff will administer the venipuncture and attempt to mitigate any associated risks.

Rectal Swabs: There are minimal risks associated with rectal swab collection. Some discomfort may occur.

Fingerstick (Blood smears): A lancing device will be used to obtain a small sample of blood. There are minimal risks associated with this procedure.

Temperature: Discomfort may be associated with taking the child's core body temperature.

13 Chapter 13: Data Safety and Monitoring Committee

13.1 Data and Safety Monitoring Committee Charter

This Charter is for the Data Safety and Monitoring Committee (DSMC) for the longitudinal MORDOR II Burkina Faso component.

The Charter will define the primary responsibilities of the DSMC, its relationship with other trial components, its membership, and the purpose and timing of its meetings. The Charter will also provide the procedures for ensuring confidentiality and communication, statistical monitoring guidelines to be implemented by the DSMC, and an outline of the content of the Open and Closed Reports that will be provided to the DSMC.

13.2 Primary Responsibilities of the DSMC

The DSMC will be responsible for safeguarding the interests of trial participants, assessing the safety and efficacy of the interventions during the trial, and monitoring the overall conduct of the trial. The DSMC will provide recommendations about stopping or continuing the trial. To contribute to the integrity of the trial, the DSMC may also formulate recommendations relating to the selection/recruitment/retention of participants, to protocol-specified regimens, and the procedures for data management and quality control.

The DSMC will be advisory to the trial leadership group, hereafter referred to as the Steering Committee (SC). The SC will be responsible for promptly reviewing the DSMC recommendations and determining, whether to continue or terminate the trial, and to determine whether amendments to the protocol are required. If needed, the DSMC may seek the advice of a content expert outside of the committee.

13.3 DSMC Membership

The DSMC is an independent multidisciplinary group consisting of epidemiologists, biostatisticians, bioethicists, and clinicians that collectively has experience in pediatrics, the management of infectious diseases, and in the conduct and monitoring of randomized clinical trials including subsaharan Africa.

13.4 Conflicts of Interest

The DSMC membership has been restricted to individuals free of apparent conflicts of interest. The source of these conflicts may be financial, scientific, or regulatory. Thus, neither study investigators nor individuals employed by the sponsor, nor individuals who might have regulatory responsibilities for the trial products, are members of the DSMC.

The DSMC members will disclose to fellow members any consulting agreements or financial interests they have with the sponsor of the trial, with the contract research organizations (CRO), or with other

sponsors having products that are being evaluated or that are competitive with those in the trial. The DSMC will be responsible for deciding whether these consulting agreements or financial interests materially impact their objectivity.

The DSMC members will be responsible for advising fellow members of any changes in any of the membership requirements that occur during the course of the trial. It may be appropriate for DSMC members who develop significant conflicts of interest resign from the DSMC.

DSMC membership is to be for the full duration of the trial. If any members leave the DSMC, the SC, in consultation with the DSMC, will promptly appoint a replacement.

13.5 Timing and Purpose of the DSMC Meetings

Organizational Meeting

The initial meeting of the DSMC will be an Organizational Meeting. This is during the final stages of protocol development and the purpose is to provide advisory review of scientific and ethical issues relating to study design to discuss the standard operating procedures and to discuss the format and content of the Open and Closed Reports that will be used to present trial results.

The Organizational Meeting will be attended by all DSMC members, lead trial investigators, and the trial biostatistician. The DSMC will be given the drafts of the trial protocol, the Statistical Analysis Plan, the DSMC Charter, and the current version of the case report forms. At subsequent meetings, committee members will receive Open and Closed Data Reports.

13.6 Procedures to Ensure Confidentiality and Proper Communication

To enhance the integrity and credibility of the trial, procedures will be implemented to ensure the DSMC has access to all emerging information from the trial regarding comparative results of efficacy and safety, aggregated by treatment arm.

Closed Sessions

Sessions involving only DSMC members and, where appropriate, those unmasked trial investigators (on the Data Coordinating Committee) who generate the Closed Reports (called Closed Sessions) will be held to allow discussion of confidential data from the trial, including information about the relative efficacy and safety of interventions.

At a final Closed Session, the DSMC will develop a consensus on its list of recommendations, including that relating to whether the trial should continue.

Open Session

In order for the DSMC to have access to information provided, by study investigators, or members of regulatory authorities, a joint session between these individuals and DSMC members will be held between the Closed Sessions.

Open and Closed Reports

For each DSMC meeting, Open and Closed Reports will be provided. Open Reports, will include data on recruitment and baseline characteristics, pooled data on eligibility violations, and completeness of followup and compliance. The study statistician ([name]) will prepare these Open Reports.

Closed reports, available only to those attending the Closed Sessions of the meeting, will include analyses of primary and secondary efficacy endpoints, including subgroup and adjusted analyses, AEs and symptom severity, , and Open Report analyses that are displayed by intervention group. These Closed Reports will be prepared by the study biostatistician.

The Open and Closed Reports should provide information that is accurate, with follow-up that is complete to within two months of the date of the DSMC meeting. The Reports should be provided to DSMC members approximately three days prior to the date of the meeting.

Minutes of the DSMC Meeting

The research team will prepare minutes for the open portion of the meeting, including the DSMC's recommendations.

Recommendations to the Steering Committee (SC)

At each meeting of the DSMC during the trial, the committee will make a recommendation to the Steering Committee to continue or terminate. This recommendation will be based primarily on safety and efficacy considerations and will be guided by statistical monitoring guidelines defined in this Charter.

Recommendations to amend the protocol or conduct of the study made by the DSMC will be considered and accepted or rejected by the SC. The SC will be responsible for deciding whether to continue or to stop the trial based on the DSMC recommendations.

The DSMC will be notified of all changes to the protocol or to study conduct. The DSMC concurrence will be sought on all substantive recommendations or changes to the protocol or study conduct prior to implementation.

The SC may communicate information in the Open Report to the sponsor and may inform them of the DSMC recommended alterations to study conduct or early trial termination in instances in which the SC has reached a final decision agreeing with the recommendation. The SC will maintain confidentiality of all information it receives other than that contained in the Open Reports until after the trial is completed or until a decision for early termination has been made.

13.7 Statistical Monitoring Guidelines

The SC will propose statistical rules for a futility stopping rule (requested by the sponsor) and an efficacy stopping rule at the first DSMC meeting. A decision will be made whether the efficacy stopping rule is appropriate for the study.

14 Chapter 14: Study Team Roles and Responsibilities

- Investigators (UCSF): UCSF will be responsible for study design and implementation, data management and monitoring, data analysis, and dissemination of results. The UCSF investigators will design and implement trainings for study procedures and maintain frequent communication with local Nouna study staff
- Investigators (Nouna): The Nouna investigators will contribute to the study design, implementation, data management and monitoring, data analysis, and dissemination of the results. The Nouna team will oversee all local study activities, including training and regular supervision and monitoring of all local study staff.
- Medical Monitor: The Medical Monitor will provide clinical oversight for the enrolled children. Study team members will report serious adverse events to the Medical Monitor within 24 hours of occurrence. The Medical Monitor will determine if the event is likely to be related to azithromycin and provide clinical guidance for the adverse event as needed.
- Data and Safety Monitoring Committee: The Data and Safety Monitoring Committee will provide independent oversight of data quality and patient safety during the course of the study.
- Study Team Members (Nouna): Study team members in Nouna will be responsible for implementing all study procedures including recruitment, consent, enrollment, randomization, drug administration, and collection of all study data.
 - Hospital Staff: Hospital staff will be trained to determine the randomization allocation of each enrolled child by utilizing the study tablets and administer azithromycin if indicated
 - Outcome Assessor: One outcome assessor will be trained to manage consent, enrollment, and collection of all study data, including outcome assessments

15 Revision History

1/30/19: Addition of [name]

1/31/19: Addition of new inclusion/exclusion criteria (enrollment in NAITRE)

2/1/19: Addition of new Fresh Frozen Stool Protocol, re-formatting, addition of rectal swab risk and fingerstick risk to 11.3.1.

3/11/19: Addition of secondary outcome measure to section 3.5 of malaria. We will measure core body temperature as well as blood smears. Addition of temp to 3.6 participant timeline, chapter 3 baseline information, 7.2 temperature protocol, 11.3 discomfort as risk added

3/14/19: Addition of rectal swab collection in 20 randomly selected children at day 2,4,6,8,10, 12 after treatment. Addition of Chapter 4 to better describe procedures

4/15/19: Change study site information. Will only enroll at Nouna hospital now. Addition of [name]. Section 4.6-Addition of rdt and referral if child has a fever

5/30/19: Rectal swab group no longer has other procedures done. Changes made to section 3.5, 3.6, Chapter 4 Table 1, 4.3, and 6.2.

7/3/19: Removal of the following exclusion criteria:

- Antibiotic use in the past 7 days
- Clinical complications requiring antibiotic treatment
- Clinical complications requiring inpatient treatment
- Congenital abnormality or chronic debilitating illness that would lead to predictable growth faltering or reduce likelihood of treatment benefit (such as cerebral palsy, Down syndrome, congenital heart disease, cleft lip/palate, etc.)

7/19/2019: Rewording for 3.1.1. Removed the word "census" and replaced with "mobilize" 7/29/2019: Changed the sample size for the supplementary rectal swab group from 25 to 50. Edited Figure 1, Table 1, Sections 3.0, 4.3, and 6.2. Also deleted in section 3.4 the sentence "we will ask about baseline antibiotic consumption."

8/30/2019: Addition of [name], [name], [name] as authors. Addition of RECTAL primary and secondary outcomes (Section3.5). Addition of RECTAL objective (section 1.2). 9/10/2019: Removal of "home" rectal swabs. Rectal swabs will be collected at home OR at the hospital for the rectal cohort of 50 kids.

10/3/2019: Addition of [name]

11/26/2019: Addition of [name], [name], [name], [name]

3/18/20: Increase sample size (section 1.4, Chapter 3 diagram, 3.2)

3/20/2020: Addition of 6 month window (120-210 days

2/10/21: Addition of RDT used to section 4.6, addition of 4.8 "Stool" because this section was mistakenly omitted , addition of language to Chapter 7 regarding children unable to produce stool.

7/1/21: Addition of 2 year follow-up timepoint with a rectal swab collection.

16 References

MORDOR Project

October 20, 2021 Version 1.7

Statistical Analysis Plan

UCSF Francis I. Proctor Foundation Centre de Recherche en Santé de Nouna University of Heidelberg

Introduction

This document (Statistical Analysis Plan, SAP) describes the planned analysis and reporting for the clinical trial, **GAMIN: Gut and Azithromycin Mechanisms in Infants and Neonates in Burkina Faso**. It includes specifications for the statistical analyses and tables to be prepared for the interim and final Clinical Study Report. This study is a Phase IV clinical trial to compare methods to reduce childhood mortality using mass administration of azithromycin (Pfizer, CAS 83905-01-5) compared to placebo. The content of this Statistical Analysis Plan meets the requirements stated by the US Food and Drug Administration and conforms to the American Statistical Association's Ethical Guidelines.

The following documents were reviewed in preparation of this Statistical Analysis Plan:

- Azithromycin for the reduction of child and infant mortality: Longitudinal Component, Manual of Operations and Procedures
- Azithromycin for the prevention of neonatal mortality in Burkina Faso: an individualrandomized trial, Statistical Analysis Plan
- Statistical Analysis Plan, MORDOR Trial
- ICH Guidance on Statistical Principles for Clinical Trials

The planned analyses described in this SAP will be included in future manuscripts. Exploratory analyses not necessarily identified in this Statistical Analysis Plan may be performed to support the analysis. Unplanned analyses not delineated in this Statistical Analysis Plan will be documented as such in the final Clinical Study Report and manuscripts. Note that unplanned analyses will be broadly grouped into two categories:

- 1. Sensitivity analyses for pre-specified outcomes
- 2. Other unspecified analyses

Sensitivity analyses are defined as alternate ways of modeling the primary outcome to ensure the finding was not dependent on the analytic plan, and these will not be subject to a multiple comparisons correction. Other unspecified analyses will be declared hypothesis generating or subject to an alpha level of 0.001.

This document will be reviewed prior to the enrollment of patients. All subsequent changes will be indicated by detailed change log in the Appendix.

Contents

1	Summary	5
	1.1 Longitudinal Trial	5
2	Statistical Analysis	5
	2.1 Planned Analyses	5
	2.1.1 Longitudinal Trial	5
3	Sample Size Considerations	7
4	Randomization	7

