1.2 Objectives

1:

To determine the effect of a single dose of azithromycin for children aged 8 days-59 months on longitudinal changes in the intestinal microbiome over a 6-month period. We hypothesize that a single dose of azithromycin will result in a significant difference in the intestinal microbiome within the treatment group compared to the placebo group after a 6-month period within children ages 8 days-59 months.

2: To determine the effect of a single dose of azithromycin for children aged 8 days-59 months on child growth over a 6- month period. We hypothesize that a single dose of azithromycin will increase child growth over a 6-month period in children aged 8 days-59 months.

3. To determine the effect of a single dose of azithromycin for children aged 8 days to 59 months on the presence of macrolide genetic resistance determinants within the first two weeks post-

treatment. The investigators hypothesize that a single dose of azithromycin will increase the presence of macrolide resistance determinants over a 2-week period in children aged 8 days to 59 months.

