3.5 Outcomes

Primary Outcome

- Changes in intestinal microbiome over a 6-month period (Objective 1). Microbiome diversity will be measured at all follow-up time points.
 - Whole Blood Venipuncture. Whole blood venipuncture will be collected at all follow-ups. We will measure cell-free DNA and inflammatory markers such as C-reactive protein.
 - **Nasopharyngeal Swabs.** NP swabs will be collected at all follow-up time points. We will collect data on phenotypic resistance of *S. pneumoniae*, evaluate the microbiome using next-generation sequencing, and monitor genotypic resistance among various organisms.
 - **Fresh Frozen Stool**. FFS will be collected at all follow-ups. We will be looking for IgA-bound bacteria from the small intestine and evaluating inflammatory markers such as C-reactive protein.

- **Rectal Swabs**. We will collect rectal swabs at all time points. We will monitor genotypic resistance of various organisms with targeted PCR and evaluate the microbiome using next-generation sequencing.
- **Presence of macrolide genetic resistant determinants (Objective 3).** Macrolide resistance will be measured from a sample of participants.
 - Rectal Swab Cohort. We will collect rectal swabs from 50 children at days 0, 2, 4, 6, 8, 10, 12, 14 and 180 post-treatment. Macrolide resistance will be analyzed using DNA sequencing.
 - **2 Year Timepoint.** We will collect rectal swabs from all kids 2 years postenrollment to evaluate macrolide genetic resistance determinants.

Secondary Outcomes

- Child growth over a 6-month period (Objective 2). Anthropometry measurements will be collected at all follow-up time points. Weight gain will be defined as grams per kilogram per month (g/kg/month).
 - MUAC. Mid-upper arm circumference will be measured at all follow-ups
 - **WAZ.** Weight will be measured at all follow-ups and weight-for-age z-scores will be calculated
 - WHZ. Weight and height will be used to calculate weight for height z-scores
 - **HAZ.** Height or length will be measured at all follow-ups and height-for-age z-scores will be calculated.
- Mortality by 6-months. Vital status will be assessed at all follow-up visits. Mortality will be defined as death within the study period. Date of death will be collected.
- Adverse events. Adverse events will be reported at all follow-ups.

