4.11 Summary of Sample Collections

Organism/Outcome	Test	Sample	Time Point (Days)			Processing
		-	0	14	180	Site
Malaria	Thick and Thin Blood Smears	Finger stick	\checkmark	1	✓	Nouna
Phenotypic resistance: S. pneumoniae	Kirby Bauer (or Etest)	NP swabs	\checkmark	~	~	Nouna
Genotypic resistance: E. coli , S. pneumoniae , S. aureus , Campylobacter spp Klebsiella spp	Targeted PCR: erm, mef, mph	Rectal and NP swabs	~	1	1	UCSF
Microbiome	Next-generation sequencing	Rectal and NP swabs	1	1	1	UCSF
Inflammatory markers	C-reactive protein	Whole blood and frozen stool	\checkmark	~	~	Nouna and/or Gates labs
IgA-bound bacteria from small intestine	BugFACS	Whole blood and frozen stool	~	1	1	Gates labs
Nutritional status	Anthropometric measurements	Weight, height, MUAC	~	1	~	Nouna
Vital status	Mortality, hospitalization	Caregiver questionnaire		✓	1	Nouna

Summary of laboratory and other assessments in Nouna longitudinal study

5 Chapter 5: Study Medication

Enrolled participants will be offered weight-based, directly observed, oral suspension azithromycin or placebo. Adverse events will be monitored.

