2.1 Planned Analyses

2.1.1 Longitudinal Trial

Four hundred fifty children between the ages of 8 days and 59 months may be enrolled in the trial and be offered placebo or azithromycin in a masked fashion. Relevant indicators will be collected using whole blood venipucture, nasopharyngeal swabs, fresh frozen stool, rectal swabs, and anthropometry measurements at days 0, 14, and 180. Children followed up within day 120 and day 240 will be included in primary day 180 analysis. Fifty randomly selected children (25 per arm) will have an additional rectal swab collected at days 2, 4, 6, 8, 10, 12 post-treatment.

Primary Analyses. Pairwise comparison of *Campylobacter*, *C. upsaliensis* and *C. hominis* using Fisher's exact test, corrected for multiple comparisons using Holm-Bonferroni method.

We will compare profile of *Campylobacter*, *C. upsaliensis* and *C. hominis* based on L_1 , L_2 distance, and PERMANOVA. We will compare diversity between arms at days 14 and 180 separately, using Shannon's Index and Simpson's Index.

Statistical considerations.

- Model adequacy will be checked by examination of residuals or other goodness of fit tests as needed. Inadequate model fit will prompt us to report alternative models.
- Multiple imputation will be used in case of missing baseline covariates (if applicable). Missing outcome variables will be handled by sensitivity analysis and reporting of conditional results.
- False Discovery Rate will be calculated for each estimated significant effect.

Secondary analyses.

Note that participants outside of WHO Child Growth Standards for WAZ (-6 to +5 SD), HAZ (-6 to +6 SD), or WHZ (-5 to +5 SD) will be excluded from all anthropometric analyses.

S. pneumoniae carriage and macrolide resistance Separate Fisher's exact test at days 14 and 180.

lytA occurence Separate Fisher's exact test at days 14 and 180.

erm B, mef A, pp2A Separate Fisher's exact test at days 14 and 180.

N. meningitides, H. influenzae, Moraxella, S. aureus Pairwise comparison of organisms using Fisher's exact test, corrected for multiple comparisons using Holm-Bonferroni method.

PERMANOVA of L_1 and L_2 distance of bacterial reads. Shannon's and Simpson's estimated gamma diversities will be compared by arm.

Malaria Fisher's exact test of parasitemia and clinical malaria at days 14 and 180.

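### The SAP has no analysis of Objective 3's rectal-swab sequencing outcome, listed as primary in the protocol, so its rule for unplanned analyses would make it hypothesis-generating or test it at alpha 0.001

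*SAP*

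**What the plan says.** **Protocol.** Section 1.2 gives Objective 3 a directional hypothesis, that one dose will "increase the presence of macrolide resistance determinants over a 2-week period in children aged 8 days to 59 months". Section 3.5 lists "Presence of macrolide genetic resistant determinants (Objective 3") under the Primary Outcome heading, with two components:

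- The cohort: "We will collect rectal swabs from 50 children at days 0, 2, 4, 6, 8, 10, 12, 14 and 180 post-treatment", with resistance read by DNA sequencing.
- A rectal swab from every child at 2 years, "to evaluate macrolide genetic resistance determinants".

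Section 4.11 separately lists "Targeted PCR: erm, mef, mph" on both rectal and nasopharyngeal swabs at days 0, 14 and 180.

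**SAP.** Section 1.1 has two objectives, microbiome and growth. The primary analyses in 2.1.1 cover *Campylobacter* species and Shannon and Simpson diversity. The SAP records that 25 children per arm give extra rectal swabs on days 2 to 12, but attaches no resistance endpoint, test or time point to them, and it does not mention the 2-year visit. Its resistance items are secondary: pneumococcal carriage and macrolide resistance, and "erm B, mef A, pp2A Separate Fisher's exact test at days 14 and 180". The Introduction divides unplanned analyses into sensitivity analyses of pre-specified outcomes and everything else, and for the latter says "Other unspecified analyses will be declared hypothesis generating or subject to an alpha level of 0.001".

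**The concern.** The protocol asks a primary-level question about gut resistance, and the SAP does not plan to answer it. Two things follow.

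First, the gene list, the day, the summary across days and the test for the cohort are all open and could be settled after the data are known. Second, the SAP's own classification puts an analysis it does not set out into its residual category. That strips the outcome of confirmatory standing or holds it to an alpha one fiftieth of the conventional 5% (0.05 / 0.001 = 50), in a cohort of 25 per arm.

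The direction of the hypothesis makes this more than tidiness. A rise in resistance is what the investigators expect and would need to report, and a stricter threshold makes a real rise easier to miss.

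**Working it through.** **1. Is the gap explained by timing?** The protocol's revision history adds the rectal-cohort primary and secondary outcomes on 8/30/2019 and the 2-year visit on 7/1/21. SAP version 1.7 is dated October 20, 2021, after both. The SAP's 13 Jan 2020 revision updated this sub-study's sample size, so the SAP covers the sub-study. Neither document mentions a separate SAP for it. Timing does not explain the omission.

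**2. Does the erm/mef line fill it?** The line names no specimen. It sits after pneumococcal carriage and lytA and before *H. influenzae* and *Moraxella*, and protocol 6.1 ties ermB and mefA to nasopharyngeal isolates. A nasopharyngeal reading is the natural one. A rectal reading is possible, because protocol 4.11 runs erm/mef PCR on rectal swabs too. Even then the test is secondary and covers two days. It omits mph and includes pp2A, which the 4.11 row does not list. It does not cover the sequencing series of the first two weeks or the 2-year swab.

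**3. Does the sensitivity-analysis exemption apply?** It covers alternative models of the primary outcome. The SAP has no primary analysis of Objective 3 to vary, so the exemption has nothing to attach to.

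**4. What would alpha 0.001 cost?** Neither document gives a sample size, power or prevalence for Objective 3, so there is no plan figure to reproduce. Inputs: n = 25 per arm (SAP 2.1.1), alpha 0.001 (SAP Introduction), a conventional two-sided 0.05 as comparator (assumed), complete data and individually processed samples (assumed), prevalences as shown (assumed).

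Power = sum over all (x, y) of Bin(x; 25, p1) × Bin(y; 25, p2) for which the two-sided Fisher p is at most alpha.

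| Prevalence, placebo v azithromycin | Power at 0.05 | Power at 0.001 |
|---|---|---|
| 10% v 50% | 83% | 34% |
| 20% v 60% | 79% | 25% |
| 30% v 70% | 78% | 23% |
| 30% v 80% | 95% | 53% |
| 20% v 80% | 99% | 82% |

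In counts: if one arm has no positives, 6 of 25 in the other gives p = 0.022, while 9 of 25 gives 0.0016 and 10 of 25 gives 0.0006. So 10 are needed instead of 6.

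**5. The 2-year component.** It covers all children. At the SAP's 225 per arm, 30% v 50% has 83% power at 0.001. After the 15% loss assumed in protocol 3.2 (225 × 0.85 = 191), it has 73%. These also assume individual samples.

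**6. Pooling.** SAP section 4 groups samples in fives within arm and time point and does not say whether the cohort is exempt. If it is not, 25 / 5 = 5 pools per arm. The smallest two-sided Fisher p for 5 v 5 is 2 / C(10,5) = 2 / 252 = 0.0079, so 0.001 could not be reached by that test whatever the result.

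**The case against.** **Primary status is not uniform across the protocol.** Section 3.2 sizes the trial on Simpson's diversity and calls that the primary outcome. Table 1 attaches the primary outcome to day 180. The revision history speaks of rectal primary and secondary outcomes, which fits a primary outcome of the sub-study. This is fair, and it bears on where Objective 3 belongs in the hierarchy. It does not remove the need for a planned analysis, since 3.5 lists the outcome under Primary Outcome without qualification.

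**The 0.001 rule is written for unplanned analyses.** Applying it to an outcome that the protocol pre-specifies is an inference. That stands as a caution, but the SAP defines unplanned by what the SAP itself does not set out, and it makes no exception for protocol outcomes.

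**A reader might infer that the SAP plans no resistance-gene analysis at all.** The documents do not support that, because the erm/mef line exists and could be read as including rectal swabs. A reader might also infer that no confirmatory claim is possible, or that a real rise would probably be missed. The first fails because the rule allows testing at 0.001. The second depends on the assumed prevalences: power there runs from 23% to 82% in the table above, and the 2-year comparison is larger.

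**The choice of day is open.** Objective 3 speaks of the first two weeks, so day 14 is one defensible choice among several.

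**Conclusion.** The concern holds in this form: the rectal-swab sequencing outcome of Objective 3, listed as primary in protocol 3.5, has no planned analysis in SAP version 1.7, at two weeks or at 2 years. That follows from the text alone and needs no assumption.

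The consequence, that the outcome becomes hypothesis-generating or is tested at 0.001, follows from a literal reading of the SAP's rule. Its size at 25 per arm is uncertain because no prevalences are given. Across the effects tried, power drops by 17 percentage points (99% to 82%) to 55 (78% to 23%). The figures rest on a 5% comparator, complete data and individual samples. If the cohort is pooled in fives, Fisher's test on pools cannot reach 0.001 at all.

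**What to change.** - Add Objective 3 to SAP 1.1 and 2.1.1 as a pre-specified analysis outside the 0.001 rule, and state its place in the multiplicity plan.
- Define the endpoint as macrolide resistance determinants in rectal swabs by DNA sequencing, with a named time point inside the two-week window. Day 14 adjusted for the day-0 swab, with days 2 to 12 as support, would serve.
- Specify a separate 2-year comparison.
- State whether the five-sample pooling applies to these samples. If it does, the pool is the unit of analysis, not the child.
- Name the specimen on each resistance line and reconcile the gene list with protocol 4.11, including mph and pp2A.
- Date the amendment and state whether it preceded sight of unmasked resistance results. If it did not, label the analysis post hoc.

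**Cost.** Mostly SAP text, since the swabs and sequencing are already in the protocol. It adds one more primary-level comparison to the multiplicity plan. If pooling does cover the cohort, per-child results would need a change in laboratory processing, while a pool-level analysis needs only wording but leaves 5 units per arm at each time point.
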